14.5. Determination of Causality

The Investigator will use medical consideration to determine the potential relationship of the AE to the study drug based on his/her clinical judgment. Assessment of causality will be based upon the following:

- Alternative possible causes of the AE, including the subject's underlying disease or comorbid conditions, other drugs, and environmental factors
- The temporal sequence between the exposure to study drug and the AE
- Whether the clinical or laboratory manifestations of the AE are consistent with known actions or previously reported toxicity of the study drug or similar drugs

- Whether the AE resolved or improved with decreasing the dose or stopping the study drug (*i.e.*, dechallenge); or recurred or worsened with re-exposure to the drug (*i.e.*, rechallenge)

Relationship assessments that indicate “Not Related” to study drug:

- **Unrelated:** The event is related to an etiology other than the study drug (the alternative etiology must be documented in the study subject’s medical record and/or SAE form).
- **Unlikely related:** The event is unlikely to be related to the study drug and likely to be related to factors other than study drug.

Relationship assessments that indicate “Related” to study drug:

- **Possibly related:** There is an association between the event and the administration of the study drug and there is a plausible mechanism for the event to be related to study drug; but there may also be alternative etiology, such as characteristics of the subject’s clinical status or underlying disease.
- **Probably related:** There is an association between the event and the administration of study drug, a plausible mechanism for the event to be related to the study drug and the event could not be reasonably explained by known characteristics of the subject’s clinical status or an alternative etiology is not apparent.
- **Related:** There is an association between the event and the administration of study drug, a plausible mechanism for the event to be related to the study drug and causes other than the study drug have been ruled out and/or the event re-appeared on re-exposure to the study drug.

For any untoward medical occurrence that starts before administration of study drug, only those that are assessed by the Investigator as protocol related should be reported to the Sponsor as an adverse event. If deemed unrelated to a study-specific procedure, the event should be added to the Medical History eCRF.

The following guidelines should be used by Investigators to assess the relationship of an untoward medical occurrence to a protocol required procedure:

- **Protocol-related:** The event occurred due to a procedure or intervention that was described in the protocol for which there is no alternative etiology present in the subject’s medical record.
- **Not protocol-related:** The event is related to an etiology other than the study procedure (the alternative etiology must be documented in the study subject’s medical record).

14.6. Documenting Adverse Events

All AEs, including SAEs, are to be accurately recorded on the Adverse Event page of the subject’s electronic CRF from the time the subject signs the ICF or assent form through the initial follow-up period (Day 56). AEs that are ongoing at the end of the Initial Follow-up Period and are considered drug related should be followed until resolution or no resolution is expected.

Each event will be assessed for serious criteria, severity, and causality. The date of onset, as well as the duration of the event will be recorded. In addition, treatments provided to the subject, actions taken with the study drug, and the outcome of the AE will also be noted.

14.7. Reporting Dose-Limiting Toxicities and Serious Adverse Events

Time Frame for Reporting

All DLTs and SAEs must be reported to the Sponsor or Sponsor designee within 24 hours of awareness, regardless of initiation of new anticancer therapy, including the following:

- Any death or SAE experienced by the subject from the signing of informed consent through the initial follow-up period (Day 56), regardless of relationship to study drug.
- Any death or SAE that the Investigator becomes aware of, and believes to be study drug related, that occurs beyond Day 56.

[REDACTED]

[REDACTED]

[REDACTED]

[REDACTED]

Questions or assistance with completing forms can be directed to Ziopharm Oncology, Drug Safety and Pharmacovigilance: [REDACTED]

Additional data concerning the SAE (e.g., diagnostic test reports, hospital summaries, *etc.*) must be promptly reported (within 24 hours of receipt) to the Sponsor or Sponsor's designee, until resolution of the SAE. Should the FDA or other National Regulatory Authority require that the Sponsor submit additional data on the event, the Investigator will be asked to provide those data to the Sponsor in a timely fashion.

Information to be Provided by the Investigator

Within 24 hours of becoming aware of the SAE or subject death, the Investigator must notify the Sponsor or designee and transmit information to the Sponsor or designee. Information (initial and follow-up) should be provided on a paper SAE Report form signed and dated by the Investigator. The SAE Report form and copies of source documents with subject identifiers redacted will be transmitted by fax. A hospital discharge summary should be provided if the subject was hospitalized. A SAE report will be considered final once all relevant information has been received and reviewed by the Sponsor.

The SAE report form is provided in the Investigator study files. A DLT specific form will be used to report DLTs and is also provided in the Investigator files. Please refer to the Investigator study files for instructions on how to complete these forms. The Investigator will provide all of the following information related to the event:

- Investigator identification
- Subject identification (e.g., subject number, initials, sex, and age or date of birth)

- Information regarding study drug administration (e.g., start/stop date, dose, and frequency)
- Day of SAE or DLT occurrence documentation on SAE or DLT report forms
- Description of event
- Action taken with the study drug in relation to the SAE or DLT
- Outcome of the SAE or DLT

In addition to the above information, the Investigator must provide, for each event term, an assessment of:

- Severity/intensity
- Relationship to the study drug (causality assessment)

14.8. Sponsor and Investigator Responsibility for Adverse Events

All AEs and SAEs will be reported to regulatory authorities, IRBs/IECs, and Investigators in accordance with all applicable global laws and regulations, including but not limited to CFR 312.32. The Investigator must submit all Safety Letters received from the Sponsor to his/her IRB/IEC per agreements and local requirements. The Investigator must keep copies of all safety reports/letters, including correspondence with Ziopharm and the IRB/IEC, in the study file.

14.9. Follow-Up Information for Adverse Events

Safety data will be reported from the time of consent, as applicable, through the initial follow-up period (Day 56). Ongoing drug-related AEs should be followed until resolution unless none is expected.

14.10. Pregnancies

Subjects who become pregnant during the study should immediately discontinue participation in the study. The Sponsor should be immediately notified.

An initial Pregnancy Report form and a Pregnancy Outcome Form are to be completed by the Investigator or designee. The Pregnancy Report form and the completion guidelines will be provided in the Investigator study files. Please refer to the Investigator study files for details on how to complete these forms.

14.11. Overdose

Study drug overdose of a subject, with or without associated AEs/SAEs, should be reported within 24 hours of awareness to the Sponsor (Ziopharm Oncology, Drug Safety and Pharmacovigilance, [REDACTED]). All AEs or SAEs as a result of overdose should be reported as described previously in [Section 14.6](#) and [Section 14.7](#).

15. PHARMACODYNAMIC, PHARMACOKINETIC, AND IMMUNOLOGIC ASSESSMENTS

15.1. Veledimex Pharmacokinetic Assessments

In the event that the blood volume to be drawn on a given study day would exceed the allowable amount, the Principal Investigator and Medical Monitor will discuss and determine the priority of testing to be completed to ensure patient safety.

Veledimex PK assessments will occur for all subjects during study treatment and any expansion cohorts. Whole blood samples will be collected at the time points specified in the Schedule of Veledimex Pharmacokinetic Sampling Times for Arm 1 ([Table 2](#)) and Arm 2 ([Table 3](#)).

Veledimex plasma concentrations will be determined using a fully validated liquid chromatography mass spectrometry assay.

[REDACTED]

[REDACTED]

[REDACTED]

[REDACTED]

16. STATISTICAL METHODS

This study is designed as a multicenter Phase I/II dose escalation study in pediatric subjects with brain tumors. Enrollment in Arm 1 Cohort 1 is open to subjects except those with DIPG; enrollment in Arm 2 (*i.e.*, Cohorts 3 and 4) is open to subjects with DIPG only. Cohorts will be enrolled according to a standard 3 + 3 design (see [Section 7.1](#)).

The primary analysis will be performed after all subjects complete the Initial Follow-up Period (Day 56). Additional analyses will be performed to determine ORR, PFS, and OS. The final analysis will be performed when the last subject completes two years of follow-up.

A formal statistical plan for the analysis and presentation of data from this study will be prepared prior to database lock. Deviations from the statistical analyses outlined in this protocol will be indicated in this plan; any further modifications will be noted in the final clinical study report.

16.1. Populations for Analysis

This is an amendment to an ongoing study that has been previously described. For all practical purposes the connotation of the safety population for the planned safety analysis are subjects being denoted in defining the overall safety population (OSP) defined below to distinguish this group from the subgroup of subjects denoted as the evaluable safety population (ESP) who must receive Ad-RTS-hIL-12 and at least one dose of veledimex after injection.

This distinction provides for inclusion of both drug components (Ad-RTS-hIL-12+ veledimex) in order to evaluate dose escalation via the rule-based criteria fundamental to the 3+3 method. This means that during dose escalation if at least one of three Ad-RTS-hIL-12 treated subjects does not receive at least one dose of veledimex, additional eligible subjects will be enrolled as applicable in order to achieve the samples size of three evaluable subjects to assist the SRC's evaluation when making a dose escalation or a dose de-escalation decision. Specifically,

- The OSP will be used to perform safety evaluations for all subjects who have received at least one dose of veledimex or Ad-RTS-hIL-12.
- The ESP will include subjects who received Ad-RTS-hIL-12 and at least one dose of their cohort specific-dose of veledimex after Ad-RTS-hIL-12 administration and are BSA conformant. The ESP will be used to make decisions regarding escalation to higher veledimex doses for Arms 1 and 2 separately, based on a standard 3 + 3 design, as described in [Section 7.3](#).
- The Pharmacokinetics Population (PKP) for veledimex includes all subjects who receive veledimex with sufficient PK timepoints.

Up to 30 evaluable subjects in the Phase II expansion cohort may be enrolled to provide time to OS estimation. This subgroup will include subjects treated with both Ad-RTS-hIL-12 and at least one dose of veledimex as defined by the ESP and other evaluability criteria described in the Statistical Analysis Plan.

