monitoring of the frequency and severity of adverse events. The incidence of adverse events will be tabulated and reviewed for potential significance and clinical importance.

Urine, fecal, saliva, buccal, and blood samples will be collected and tested for viral replication.

The reporting period for safety data will be from the date of ICF or assent signature through the Initial Follow-Up Period (Day 56).

Evaluation at the Recommended Phase II Pediatric Veledimex Dose:

A decision to enroll additional subjects as part of an expansion cohort will be made by the SRC.

Criteria for Evaluation:

Tumor Response Assessments and Overall Survival:

The ESP will be evaluated for Investigator assessment of ORR, PFS, and OS. Response will be assessed using the baseline (Day 2 ± 24 hours) Immunotherapy Response Assessment for Neuro-Oncology (iRANO) criteria used to characterize tumor response assessments. In the absence of a pediatric RANO criteria, adult response criteria will be used.

[REDACTED]

[REDACTED]

[REDACTED]

Pharmacokinetic Evaluations:

Veledimex PK parameters will be evaluated at each dose level in the dose escalation cohorts and in any expansion cohort(s).

Statistical Methods:

Analysis Populations:

This is an amendment to an ongoing study that has been previously described. For all practical purposes the connotation of the safety population for the planned safety analysis are subjects being denoted in defining the overall safety population (OSP) defined below to distinguish this group from the subgroup of subjects denoted as the evaluable safety population (ESP) who must receive Ad-RTS-hIL-12 and at least one dose of veledimex after injection.

This distinction provides for inclusion of both drug components (Ad-RTS-hIL-12 + veledimex) in order to evaluate dose escalation via the rule-based criteria fundamental to the 3+3 method. This means that during dose escalation if at least one of three Ad-RTS-hIL-12 treated subjects does not receive at least one dose of veledimex after injection, additional eligible subjects will be enrolled as applicable in order to achieve the samples size of three evaluable subjects to assist the SRC's evaluation when making a dose escalation or a dose de-escalation decision. Specifically,

- The OSP includes all subjects who received at least one dose of veledimex or Ad-RTS-hIL-12

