- The ESP includes all subjects who received Ad-RTS-hIL-12 and at least one dose of veledimex after Ad-RTS-hIL-12 administration, and are BSA conformant
- The Pharmacokinetics Population (PKP) includes all subjects who received veledimex with sufficient timepoints

Safety Analysis:

The OSP will be used to perform safety evaluations for all safety variables.

The ESP will be used to make decisions regarding escalation to higher veledimex doses for Arm 2, the rule-based criteria of a 3 + 3 design, as previously described.

For the first (10 mg) veledimex dose cohorts in Arms 1 and 2 (*i.e.*, Cohorts 1 and 3, respectively), a minimum of three ESP subjects must be eligible for evaluation of safety. In addition, evaluation of any DLTs will be performed according to protocol-defined criteria.

Safety variables will be tabulated and presented by arm and by dose cohort. Exposure to study drug(s) and reasons for discontinuation of study treatment will be tabulated. All treatment-emergent adverse events (TEAEs) will be coded according to the System Organ Class and Preferred Term using the Medical Dictionary for Regulatory Activities (MedDRA). The TEAEs will be tabulated by the number and percent of subjects according to relationship to study drug(s), severity, and seriousness. Laboratory parameters will be summarized by visit. Vital signs and physical examination data will be listed by visit.

Tumor Response and Overall Survival Analyses

If an SRC committee decision results in enrolling subjects into an expansion cohort, the primary analysis for tumor response variables and OS will be performed on the ESP population. Secondary analyses will include all treated subjects as defined by the safety population denoted the OSP. The Investigator assessment of ORR and PFS will be determined for each cohort. The OS is defined as the duration of time from the first dose of study drug to the date of death or, for subjects who are still alive two years after first dose of study drug, subjects will be censored at the last follow-up contact date. A 2-sided confidence interval will be computed for the ORR. The PFS and OS will be analyzed using Kaplan-Meier methods. If an expansion cohort to treat up to 30 subjects is not performed, instead of a statistical analysis of data from very small sample sizes, listings of the investigator assessment of ORR and PFS by subjects will be constructed on the subjects treated during the dose escalation phase.

PK, [REDACTED]

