Arm 1: This study has been modified to explore one veledimex dose in Arm 1: 10 mg.

Arm 2: This study is designed to explore two veledimex doses in Arm 2: 10 mg and 20 mg. Subject enrollment and veledimex dose escalation will proceed according to a standard 3+3 design. The first cohort will receive 10 mg veledimex followed by the second cohort receiving 20 mg veledimex.

Arm 1 and Arm 2 subjects may exhibit different safety and tolerability profiles. The 3+3 standard study design has been modified to independently evaluate the two arms separately.

The study arms and assigned doses will be divided into 3 cohorts as shown below:

Table 4a: ATI001-103 Cohorts

Arm	Cohort	Indication	Procedure	Assigned Veledimex Dose ^a
1	1	Resectable pediatric brain tumor	Craniotomy	10 mg
2	3 ^b	DIPG	Stereotactic	10 mg
2	4	DIPG	Stereotactic	20 mg

^a Doses are BSA-adjusted doses

^b Arm 1 Cohort 2 was removed in Protocol Amendment 2. The SRC reviewed the safety profile of Arm 1 Cohort 1 and determined it was appropriate to move forward with Arm 1, Cohort 2 and Arm 2, Cohort 1, however due to issues with enrollment of supratentorial patients, it was determined not to proceed with Cohort 2.

Note: After the completion of a phase I dose escalation cohort in Arm 2, the SRC may elect to expand that cohort by up to 30 DIPG patients, which will be considered the Phase II component of study.

Each cohort will consist of subjects \leq 21 years-of-age who meet eligibility criteria.

Each subject in each dose escalation cohort will be monitored for 28 days after Ad-RTS-hIL-12 injection before additional subjects are enrolled in the same cohort. The evaluation period for DLT is 28 days after Ad-RTS-hIL-12 injection (Day 0 to Day 28).

Determination of safety and the recommendation to expand the current dose cohort, dose escalate, or discontinue the investigation, will occur after all dosed subjects in a cohort have been evaluated for at least 28 days after Ad-RTS-hIL-12 injection, as described in Section 7.3.

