In addition to recommending dose escalation, cohort expansion, or discontinuation of treatment, as noted above, the SRC may recommend dose de-escalation at any point based on safety review.

Dose De-Escalation

If it is determined that dose escalation or cohort expansion should not proceed, dose de-escalation may be undertaken and the SRC will consider de-escalating the veledimex dose as follows:

- De-escalation by increments of 5 mg from the cohort in which 2 or more DLTs were observed (*e.g.*, 15 mg, de-escalated from 20 mg)
- If there are 2 or more DLTs in the dose de-escalation cohort, the SRC will consider stopping enrollment at that dose and de-escalating the veledimex dose by an additional increment of 5 mg (*e.g.*, 5 mg down from 10 mg) or declaring a previously studied dose level the recommended Phase II pediatric dose

If no DLTs occur among the three subjects in Cohort 1, dosing may proceed to the next cohort, Cohort 3, after the SRC provides their recommendation to proceed (Table 5). In any cohort, if one DLT occurs among the three subjects, three additional subjects will be enrolled. If one or more of the three additional subjects experience a DLT, dosing will stop. The SRC will then convene to evaluate safety, determine if the recommended Phase II dose has been reached per **Section 7.5**, and will decide whether to stop treatment or de-escalate veledimex dosing. The SRC may also seek an *ad hoc* safety evaluation and recommendation by external experts as needed.

Table 5: Dose Escalation and De-Escalation Decision Rules

Subjects with DLTs (Any Dose Level)	Decision Rule	Subject Count
None of the first 3 subjects OR ≤ 1 subject (in the case of a 6-patient cohort) experiences a DLT	Expand current dose level cohort or enroll the next higher dose level cohort (after SRC recommendation).	3 or 6
1 of the first 3 subjects experiences a DLT	Enroll at least 3 more subjects in this dose level cohort. If none of the 3 additional subjects experiences a DLT, expand current dose level cohort or proceed to the next planned dose level cohort (after SRC recommendation).	6

Table 5: Dose Escalation and De-Escalation Decision Rules (Continued)

Subjects with DLTs (Any Dose Level)	Decision Rule	Subject Count

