2 or more subjects in a cohort experience a DLT	
If 2 subjects experience a DLT, then STOP dose escalation in the cohort experiencing the DLTs and do the following:
 
 The SRC will conduct a safety review to evaluate safety and determine whether the cohort experiencing the 2 DLTs has met the definition of the recommended Phase II pediatric veledimex dose (Section 7.5). Based upon this review, the SRC will make a recommendation that the cohort either continue at the existing dose, at a lower dose level, or other measures to be undertaken including discontinuation of treatment. If it has been determined that escalation or cohort expansion should not proceed, dose de-escalation may be undertaken and the SRC will consider de-escalating the veledimex dose as follows: 
 De-escalation by increments of 5 mg from the cohort in which 2 or more DLTs were observed (e.g., 15 mg down from 20 mg). If there are 2 or more DLTs in the dose de-escalation cohort, the SRC will consider de-escalating the veledimex dose by additional increments of 5 mg (e.g., 5 mg down from 10 mg) or declaring a previously studied dose level the recommended Phase II pediatric dose. 	2 to 6

After completion of a cohort, if it has been determined that the recommended Phase II pediatric dose has not been reached, escalation to the next cohort will proceed once recommended and authorized by the SRC.

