7.5. Recommended Phase II Pediatric Veledimex Dose and Corticosteroid Exposure

The recommended Phase II pediatric veledimex dose will be determined using the Evaluable Safety Population (ESP). The recommended pediatric Phase II dose is defined as the dose level below the dose in which $\geq 33\%$ of subjects in the same cohort experience DLTs. If 2 DLTs occur in the same cohort, dose escalation will stop in the cohort experiencing the DLTs. A decision to enroll additional subjects in an expansion cohort will be made by the SRC.

The recommended pediatric Phase II dose in this study will be determined in the context of variable corticosteroid exposure and will be reported as such. Investigational treatment requires that steroid use be allowed to manage brain tumor related symptoms or edema, especially after tumor resection. It is expected that the use and dose of corticosteroids will vary among trial sites and among subjects, and therefore, the extent and dose of steroids is not specified in this protocol. The treating physician should consider the minimum starting steroid dose for study subjects, if determined that it is safe and appropriate for that individual subject. For study subjects who require a higher starting steroid dose, efforts should be made to taper steroids to the lowest amount that controls the subjects' symptoms, as determined to be safe and appropriate by the treating physician.

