7.6. Dose Modification and Dose Delays

Treatment dose delays and dose reductions for individual subjects will be allowed in the event of toxicities, according to the criteria shown in [Table 6](#). If a drug-related Grade 3 or higher AE occurs (excluding nausea and/or vomiting in subjects who did not receive optimal treatment with anti-emetics), the Investigator in conjunction with the Sponsor's Medical Monitor will decide whether the subject will remain on the study. The withheld doses will not be made up; the subject may be allowed to complete dosing according to the remaining schedule.

As mentioned in [Section 7.4](#), fatigue, seizures, headaches, and cerebral or pontine edema are commonly observed in this population and will be recorded according to grade of toxicity, but

will not be considered a DLT unless a relationship to study drug is deemed to be the main contributory factor. If $\geq 33\%$ of subjects experience DLTs, the SRC will convene to determine the course of action. The Medical Monitor or Investigators may request a meeting of the SRC at other times, as deemed clinically indicated.

Table 6: Criteria for Dose Delay and Dose Reduction

Event	Course of Action
Any local injection reaction that requires operative intervention	Hold study drug and contact the Medical Monitor for instructions on resuming dosing
Any local injection reaction that has life-threatening consequences requiring urgent intervention or results in death	Hold study drug and contact the Medical Monitor for instruction on resuming dosing
Any drug-related Grade 3 or higher AE ^a	Hold study drug and contact the Medical Monitor for instruction on resuming dosing

^a Excluding nausea and/or vomiting in subjects who did not receive optimal treatment with anti-emetics

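### The DLT analysis set leaves out an injected Arm 2 subject whose DLT prevents every veledimex dose, and SAP 5.3 and SAP 8 disagree on who else belongs in it

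*Protocol*

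**What the plan says.** - **Membership.** Protocol Section 4: "The ESP includes all subjects who received Ad-RTS-hIL-12 and at least one dose of veledimex after Ad-RTS-hIL-12 administration, and are BSA conformant". Sections 14 and 16.1 set the same conditions.
- **Use.** Protocol 16.1 uses the ESP for escalation and points to 7.3 for the rule. Protocol 7.5 takes the recommended dose from it. SAP 5.3 lists escalation decisions and the SRC's DLT outputs among its uses, and SAP 11 lists and summarises DLTs on it.
- **Top-up.** Protocol 16.1: "if at least one of three Ad-RTS-hIL-12 treated subjects does not receive at least one dose of veledimex, additional eligible subjects will be enrolled". Section 4 ties the missing dose to the period after the injection: "does not receive at least one dose of veledimex after injection, additional eligible subjects will be enrolled as applicable".
- **Decision rule.** Protocol 7.1 says the safety determination "will occur after all dosed subjects in a cohort have been evaluated for at least 28 days after Ad-RTS-hIL-12 injection". Protocol 7.3: "In any cohort, if one DLT occurs among the three subjects, three additional subjects will be enrolled". The stop row of Table 5 applies when "2 or more subjects in a cohort experience a DLT". None of these names the ESP. Nor does the trigger in 7.6, under which, at 33% or more "of subjects experience DLTs, the SRC will convene to determine the course of action".
- **Replacement.** Protocol 8.5 and SAP 2.2.4 allow replacement of subjects who leave the study in the DLT window, but only when the reason is neither toxicity nor progression.
- **Timing.** The DLT window is Day 0 to Day 28 (Protocol 7.1, 7.4). Arm 2 takes its first veledimex on Day 1 (10.2). Table 6 in 7.6 holds study drug for a drug-related Grade 3 or higher event or for the listed local reactions.
- **SAP definition.** SAP 5.3 equates the ESP with the per-protocol set and keeps out subjects whose major deviations could confound the key efficacy endpoints. It mentions neither BSA conformance nor that veledimex must follow the injection. SAP 8 rules out dropping anyone from an analysis population on account of a deviation.

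**The concern.** DLT occurrence by cohort is part of the primary endpoint (Protocol 16.3.1). A set that requires exposure to the second drug component can lose the subject who was harmed by the first component before the second was given. The event then leaves both numerator and denominator, and the top-up rule may fill the place with another subject. With three to six subjects per cohort, one DLT can separate proceeding from enrolling three more, or proceeding from the two-DLT review.

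The second problem needs no rare event. SAP 5.3 and SAP 8 give opposite instructions on deviations for the set used for dose decisions and DLT tables. Whoever programs those tables must choose one of them.

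**Working it through.** **1. Can a subject have a DLT and be outside the ESP?** The window opens at injection on Day 0, and Arm 2 veledimex starts on Day 1. An attributable local reaction needing operative intervention is a DLT (7.4) and leads to a hold (Table 6). If no dose is given on any of Days 1 to 14, the subject never meets the ESP condition. No passage makes an exception when the DLT is the reason.

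**2. Does another passage settle it?**
- 7.1 says when the determination is made, not who is counted.
- 7.3 and Table 5 speak of subjects in the cohort without saying whether this one counts.
- 8.5 and SAP 2.2.4 bar replacement for toxicity, but only for study withdrawal. They meet the top-up rule only if the toxicity also ends study participation.

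The question is left open.

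**3. Counting examples.**
- Four injected, one such DLT, no other DLT. The fourth was enrolled to fill a place, so the affected subject is among the first three. The ESP reads 0/3, which permits expansion or escalation. If the subject counts, 7.3 calls for three more. With the subject included, the reported proportion is 1/4 = 25%.
- Seven injected, two DLTs, one of them such a case. The ESP reads 1/6 = 16.7%. If the subject counts and is not topped up, six subjects give 2/6 = 33.3%, which meets the 33% threshold and the two-DLT row. If the subject counts and was topped up, the figure is 2/7 = 28.6%: two DLTs, but below 33%.

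**4. Illustrative probabilities.** The plan states no operating characteristic to reproduce and no frequency for this case, so the rates here are assumptions. For a DLT rate x in the counted set, the rule permits proceeding with probability (1−x)³ + 3x(1−x)⁵.

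- *Assumption A:* a share f of DLT subjects is lost and topped up, so x = p(1−f)/(1−pf).

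| p | f = 0 | f = 0.05 | f = 0.10 |
|---|---|---|---|
| 0.20 | 0.709 | 0.726 | 0.744 |
| 0.30 | 0.494 | 0.516 | 0.539 |
| 0.40 | 0.309 | 0.330 | 0.351 |

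At p = 0.30, the chance of at least one lost DLT while three places fill is 1−(1−pf)³ = 4.4% (f = 0.05) or 8.7% (f = 0.10). Multiplying by (1−x)³, with x = 0.289 or 0.278, gives the chance that the ESP reads 0/3 although a DLT was lost: 1.6% or 3.3%.

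- *Assumption B:* a share r of all injected subjects has such a DLT, so x = (p−r)/(1−r). At p = 0.33 the probability moves from 0.434 to 0.505 (r = 0.05) or 0.683 (r = 0.15).

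The gain is 2.2 to 4.5 points under A at p = 0.30 and 7 to 25 points under B. The size follows the assumption, and all figures ignore SRC judgement.

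**5. SAP 5.3 against its neighbours.**
- *Deviations:* 5.3 excludes, 8 forbids exclusion. Protocol 16.1 lets the SAP add evaluability criteria for the Phase II survival subgroup, but 5.3 does not confine its clause to that subgroup.
- *Veledimex after injection:* the omission matters only in Arm 1, where a dose precedes surgery. Arm 2 has no earlier dose.
- *BSA conformance:* the omission affects only final tables, because Protocol 7.1 lets non-conformant subjects be dosed only after SRC review of the cohort.

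**The case against.** The strongest reply is that the ESP is a deliberate choice. Protocol 16.1 says both components are required so that escalation can be evaluated. The vector dose is fixed and only veledimex escalates, so a DLT before any veledimex says little about the veledimex level. This stands as a reason for an ESP-based escalation count. It does not justify leaving a protocol-defined DLT out of the DLT tables.

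A reader might infer that 7.1 and 7.3 set up a rival population and that the protocol flatly contradicts itself. The documents do not support that. 16.1 sends the ESP to the 7.3 rule, 7.1 concerns timing, and the 7.6 trigger only convenes the SRC. The fault is an unanswered question.

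The case is also narrow:
- Non-hematologic events must last at least 3 days, and transient neurological changes in Arm 2 more than 10.
- Seizures, headache and edema count only if study drug is the main contributor.
- One resumed dose restores ESP entry.
- The top-up applies where applicable and exists to assist the SRC.

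The SRC would usually learn of the event through first-subject review (7.2), 28-day staggering (7.1), 24-hour DLT reporting (7.4) or the pause in 7.10. Protocol 16.2 makes the 3+3 result one input among several, and the adverse event stays in the overall safety tables. All of this stands. But the 7.10 pause does not separately list thrombocytopenia or Grade 3 non-hematologic DLTs, and no safeguard returns the subject to the ESP count.

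The separate SRC charter might define evaluability; it is not among the documents.

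**Conclusion.** The point holds in limited form. As written, an injected Arm 2 subject whose DLT prevents every veledimex dose is left out of the reported DLT proportion and may be topped up, and the protocol does not say whether that subject counts in the 3+3 evaluation. One such subject turns a cohort with a DLT into 0/3, or two DLTs into 1/6.

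A reader might go on to infer that escalation is biased by a known amount. That is unsupported: the documents give no frequency, and two reasonable assumptions give very different gains.

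The conflict between SAP 5.3 and SAP 8 is certain and rests on no assumption, although no route is shown by which it would change a Phase I DLT count. The two dropped conditions are smaller mismatches with the protocol. Together these should be fixed before database lock; they are not a fatal flaw.

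**What to change.** 1. **SAP 11.** Report DLTs so that every BSA-conformant injected subject with a protocol-defined DLT in Day 0 to 28 is included, in numerator and denominator, whether or not veledimex was given. Show the ESP count alongside.
2. **Protocol 4 and 16.1 with 7.1, 7.3, 8.5 and SAP 2.2.4.** Reconcile these on whether such a subject counts in the 3+3 evaluation and may be topped up, and state the answer in the same words throughout. Which answer to adopt is for the sponsor and the SRC.
3. **SAP 5.3 and 8.** Remove the efficacy-deviation clause from the set used for DLTs and dose decisions, or confine it to an efficacy sensitivity set.
4. **SAP 5.3.** Restore the two protocol conditions, veledimex after the injection and BSA conformance.

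The cost is SAP rewording and a short protocol clarification, with no new data. The downside is an occasionally less favourable DLT count.
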